## C. AIM 3 (MAJOR ADVERSE EVENTS)

### 1. Primary Analysis

The study cohort in Aim 3 will be similar to the study population in Aim 1. To be eligible for Aim 3, the patient must be linked to state or national death index for mortality outcome or linked to payer data (insurance claims) for other adverse event outcomes. The primary outcome of interest will be subsequent reoperation/reintervention, defined as any additional bariatric procedure and other procedures related to device removals, gastric revisions, abdominal or incisional hernia repair, laparoscopy or laparotomy, and percutaneous endoscopic gastrostomy tube placements. Secondary outcomes of interest are (1) composite end point of 30-day major adverse outcomes, based on the definition used in the LABS study, which includes death; venous thromboembolism; percutaneous, endoscopic, or operative subsequent intervention; and failure to be discharged from the hospital, (2) any hospitalization following initial surgery, and (3) death.

Handling Pregnancy: We will ignore hospitalizations that are related to pregnancy events.

We will explore the use of the total volume of bariatric procedures (or specific bariatric procedures) by site as a potential variable for this adverse events analysis.

Primary analysis: A Cox proportional hazards model will be used to estimate the hazards ratio of each procedure type on time-to-reoperation/re-intervention for three pair-wise comparisons (RYGB vs. SG, RYGB vs. AGB, SG vs. AGB). A single Cox regression model will be estimated with RYGB as the reference procedure. Estimates of the log relative hazard of reoperation for AGB vs. SG will be calculated as the difference in each procedure's log-HR estimate (relative to RYGB) and the delta method will be used to get correct standard errors around that point estimate. The Cox regression model will also include covariate adjustment for key baseline covariates (seeaim3-descriptive-2018-05-28.xlsx for covariates to be included and factor level definitions)). In addition to reporting hazard ratios, we will report the probability of reoperation/re-intervention at 1-, 3-, and 5-years post-surgery with each procedure type for the "average" patient.

We will not adjust for propensity score decile in the outcome regression model (as in Aims 1 and 2) to simplify the analysis and interpretation of results; propensity score adjustment did not influence inference in Aims 1 and 2 and, instead, complicated presentation of the analysis and results. Estimating a single regression model (rather than three pairwise models) makes it easier to explain the estimated risk of an event at 1, 3, and 5 years for an "average" patient, since average is now defined with respect to the entire cohort rather than with respect to the subset of patients with the comparator procedures.

HTE analyses will be performed for the primary reoperation/reintervention outcome; order of HTE analysis listed at the top of analysis plan indicates priority. A sensitivity analysis will also be done where the definition of reoperation/reintervention is expanded to include endoscopy.

As a descriptive analysis, we will also report the unadjusted probability of each constituent type of reoperation and re-intervention (cholecystectomy/ostomy, conversion/revision/reversal, hernia, reoperation, vascular access, and endoscopy) at 1-, 3-, and 5-years post-surgery for each procedure type using estimates from a Kaplan Meier curve.

## 2. Secondary Analysis

Secondary analysis of time-to-event for all-cause mortality and rehospitalization will follow the same approach as the primary analysis. No HTE or sensitivity analyses will be done.

Secondary analysis of the 30-day composite AE outcome will be done with a logistic regression model. A single logistic regression model will be estimated with RYGB as the reference procedure and SG and AGB as exposures of interest. The log-odds ratio comparing SG to AGB will be calculated as the difference in the log-odds ratio comparing each procedure to RYGB, and the delta method will be used to calculate correct standard errors. (Since we only have one outcome per individual, outcomes are assumed independent conditional on covariates and we do not need to use GEE.) The logistic regression model will also be adjusted for baseline covariates and site.

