will then assess covariate overlap by comparing the PS distributions by surgery group. If patients from different surgery groups differ systematically, we will consider trimming to exclude patients that are very unlikely to be considered for the other surgery option and thus should not be included for comparative effectiveness assessment [CI-5]. We will consider using the linear mixed effects model or the generalized estimating equation model with a link to estimate the effect of surgery on percent weight changes. We will consider different PS-based analyses to adjust for confounding bias, including PS regression, matching, and inverse probability treatment weighting. For PS regression, we create a categorical variable using site-specific PS percentiles (e.g., deciles) and adjust for it in the outcome regression model. In PS matching, for each exposed subject, we use the nearest matching algorithm to find a comparable control whose PS is close to the PS of the exposed subject (e.g., the difference is less than 0.05). We then fit the outcome regression model among the matched population. In inverse probability treatment weighting, we create a weighted pseudo-population consisting of weighted copies of observed data to remove confounding bias and implement the outcome regression model among the pseudo-population. In all models, we will adjust for site in the outcome regression model to account for across-site heterogeneity. Due to the large number of comparisons, we will select a PS analysis that suits our study setting and data best considering the pros and cons of the different PS-based analyses. We will apply the analysis procedure to each imputed dataset. Suppose  $\hat{\theta}_i$  and  $\hat{W}_i \equiv \text{var}(\hat{\theta}_i)$  denote the point and variance estimates for the parameter of interest  $\theta_0$  from the  $i$ th imputed dataset,  $i = 1, 2, \dots, m$ . Then the final point estimate  $\hat{\theta} = \frac{1}{m} \sum_{i=1}^m \hat{\theta}_i$ , the average of the  $m$  complete-data estimates; and the final variance estimate  $\hat{W} = \frac{1}{m} \sum_{i=1}^m \hat{W}_i + \left(1 + \frac{1}{m}\right) \frac{1}{m-1} \sum_{i=1}^m (\hat{\theta}_i - \hat{\theta})^2$  which accounts for both within- and between-imputation variance.

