## TABLES AND FIGURES

**Table 1. Common Data Model Data Tables that are Applicable to the PCORnet Bariatric Study**

PCORnet CDM Data Table	Key Information/Description of Variables	Date Range
DEMOGRAPHIC	Key demographic variables include: Age at surgery (not date of birth), sex, Hispanic ethnicity (y/n) & race are captured.	2004 – 2016* * includes information occurring 1 year before the first bariatric procedure (2005) and one year after the last bariatric procedure (2015) in the study
ENROLLMENT	Enrollment is a concept that defines a period of time during which all medically-attended events are expected to be observed. This concept is often insurance-based, but other methods of defining enrollment are possible. Key variables include: Enrollment start and end dates, and enrollment basis (which relates to how the enrollment period was defined, e.g., insurance, geography, algorithmic, encounter)	2004 – 2016
ENCOUNTER	Contains 1 record for each time a patient sees a provider in ambulatory setting or is hospitalized; multiple encounters per day are possible if they occur with different providers or in different care settings. Encounter type will be used to identify initial bariatric procedures and all subsequent complications and procedures during the follow-up period. Encounters may also be used to determine enrollment periods. Provider, facility information, and DRGs may be used to calculate propensity scores. Key variables include: encounter ID, admit date and time, discharge date and time, provider ID (a pseudoidentifier), facility location (3 digit zip code) and ID, encounter type (ambulatory, emergency, etc), discharge disposition (which can indicate death during hospitalization), and DRG.	2004 – 2016
DIAGNOSIS	Contains all uniquely recorded diagnoses for all encounters. Each diagnosis is associated with a specific patient and encounter. Diagnosis codes and associated encounter dates will be used to establish medical history prior to surgery, to calculate propensity scores, and to identify adverse events. The main focus will be on obesity related diagnoses and adverse events, such as diabetes and hypertension. Key variables include: Diagnosis date,	2004 – 2016

	Diagnosis, diagnosis type (e.g., ICD-9, ICD-10), diagnosis source, and principal diagnosis flag	

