**Table 6. Important Baseline Covariates that will be Considered as Potential Confounders**

Variable	Source (CDM Table)	Rationale
Age*	v1.0 DEMOGRAPHIC table; Field Name = BIRTH_DATE	Choice of other surgical procedures vary with age; surgical weight loss and surgical complications likewise vary by age
Baseline BMI*	v1.0 VITAL table; Field Names = HT, WT (date of measurement: Field Name = MEASURE_DATE for each measure)	Initial BMI may shape patient and providers' procedure choice; surgical weight loss and impact on diabetes varies with anthropometric measures.
HbA1c	V2.0/3.0 LAB table; Field Name = A1C (date of measurement: Field Name = RESULT_DATE for each measure)	For Aim 2, HbA1c as a measure of glycemic control at baseline is strongly associated with risk of remission and relapse of diabetes
Diabetes Medication Use	V2.0/3.0 PRESCRIBING (and DISPENSING) table; Field Name = NDC	For Aim 2, insulin use preoperatively is strongly associated with risk of remission and relapse of diabetes  For measuring use of Diabetes Medications at baseline, we will create three variables : Insulin use Y/N, Oral medication use Y/N, and number of oral medications used
Hospital length of stay 1 year before surgery	V1.0 ENCOUNTER table; Field Names = ADMIT_DATE, DISCHARGE_DATE	This measure is another surrogate for health status, which strongly impacts procedure choice and is associated with surgical outcomes
Comorbid conditions*	v1.0 DIAGNOSIS table; Field Name = DX v1.0 CONDITION table; Field Name = CONDITION	Health status strongly impacts procedure choice and is associated with surgical weight loss and complications of surgery
Sex*	v1.0 DEMOGRAPHIC table; Field Name = SEX	Choice of surgical procedure may vary with sex, and male sex is associated with adverse outcomes
Race/ethnicity*	v1.0 DEMOGRAPHIC table; Field Name = RACE or HISPANIC	Medical/surgical treatment choices often vary with race/ethnicity as does surgical weight loss and surgery's impact on diabetes
Pre-op smoking status*	v1.0 VITAL table; Field Name = TOBACCO	Smoking status may influence procedure choice and impacts diverse health outcomes
CDRN/node site	Meta-data (CDRN of origin)	Regional eating and physical activity norms are likely to be associated with CDRN and with surgical outcomes

\* *hypothesized effect moderators*

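### Aim 3: one outcome per patient does not rule out clustering by facility or surgeon within a site, so standard errors may be too small

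*SAP*

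**What the plan says.** The 30-day composite is a secondary outcome of Aim 3, compared by odds ratio. It is analysed by one logistic regression with RYGB as reference. The SG versus AGB contrast is the difference of two log odds ratios, with a delta-method standard error. On dependence between patients the section says "Since we only have one outcome per individual, outcomes are assumed independent conditional on covariates and we do not need to use GEE", followed by "The logistic regression model will also be adjusted for baseline covariates and site". The Aim 1 primary analysis has a matching general statement: "In all models, we will adjust for site in the outcome regression model to account for across-site heterogeneity".

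The Aim 3 Cox models (reoperation/re-intervention as primary outcome; death and rehospitalization as secondary) follow the same single-model plan. Their covariates are listed in a separate spreadsheet that is not part of the document. No cluster-robust variance, random effect or stratification below site is stated for either kind of model.

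Table 1 lists, among the key variables of the ENCOUNTER table, "provider ID (a pseudoidentifier), facility location (3 digit zip code) and ID". The one analytic use given for them there is "Provider, facility information, and DRGs may be used to calculate propensity scores". For Aim 3, however, the plan says "We will not adjust for propensity score decile in the outcome regression model". Centre volume appears only as something to look into: "We will explore the use of the total volume of bariatric procedures (or specific bariatric procedures) by site as a potential variable".

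**The concern.** The stated reason does not carry the conclusion. Having one outcome per person settles whether a patient's own repeated measurements are correlated. It says nothing about two patients operated on by the same surgeon or in the same hospital. The composite includes re-intervention and failure to be discharged within 30 days, both of which can plausibly depend on local practice. Procedure choice can also follow the surgeon or facility.

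The site term absorbs average differences between sites. Table 6 takes the CDRN/node site variable from meta-data on the originating network and justifies it by regional habits of diet and exercise. The SAP does not define it as a hospital or a surgeon. Clustering inside a site is therefore left open.

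At stake is the stated precision of the Aim 3 safety comparisons. If the standard errors are too small, modest differences between procedures look more certain than they are. The delta method does not help: it passes on whatever covariance matrix the fitted model supplies, so the SG versus AGB contrast inherits any error.

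**Working it through.** The SAP gives no sample size, event rate, ICC, cluster size or interval width for this outcome, so there is no figure of its own to reproduce. The check asks how large the effect could be, on stated assumptions.

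**Inputs, all assumed.** m = patients per facility or surgeon; ICC_y = correlation of outcome within cluster; ICC_x = correlation of procedure choice within cluster. Both ICCs are what remains after site and covariates.

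**Formulas.** For a regression contrast with equal cluster sizes (an approximation):

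- design effect DE = 1 + (m − 1) × ICC_y × ICC_x
- true SE / reported SE = √DE
- coverage of a nominal 95% interval = 2Φ(1.96/√DE) − 1

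**Central case, m = 100, ICC_y = 0.01.**

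- ICC_x = 0: DE = 1; SE ratio 1.00; coverage 95.0%
- ICC_x = 0.3: DE = 1 + 99 × 0.003 = 1.30; SE ratio 1.14; coverage 91.5%
- ICC_x = 0.6: DE = 1 + 99 × 0.006 = 1.59; SE ratio 1.26; coverage 87.9%
- ICC_x = 1: DE = 1 + 99 × 0.01 = 1.99; SE ratio 1.41; coverage 83.5%

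**Range of SE ratios.**

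| m | ICC_y | ICC_x = 0 | 0.3 | 0.6 | 1.0 |
|---|---|---|---|---|---|
| 50 | 0.005 | 1.00 | 1.04 | 1.07 | 1.12 |
| 50 | 0.01 | 1.00 | 1.07 | 1.14 | 1.22 |
| 100 | 0.01 | 1.00 | 1.14 | 1.26 | 1.41 |
| 100 | 0.02 | 1.00 | 1.26 | 1.48 | 1.73 |
| 200 | 0.05 | 1.00 | 2.00 | 2.64 | 3.31 |

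If each surgeon's procedures are perfectly balanced, ICC_x is slightly negative and the ratio is 0.97 to 1.00. The model-based interval is then not too narrow.

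**Does site adjustment remove the problem?** A simulation used a logistic model with fixed site effects: 20 sites, 5 surgeons per site, 60 patients per surgeon, about 5% events, two procedures, no true procedure effect and 100 replicates per scenario. It compared the empirical SD of the log odds ratio with the mean model-based SE.

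- No surgeon effect on outcome: ratio 0.90 to 1.00.
- Surgeon effect on outcome, procedure choice unrelated to surgeon: ratio 0.99 to 1.06.
- Strong surgeon preference, latent outcome ICC 0.027: ratio 1.15; coverage 91% model-based and 91% cluster-robust.
- Strong surgeon preference, latent outcome ICC 0.099: ratio 1.29; coverage 86% model-based and 93% cluster-robust.

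With 100 replicates the simulation error is about 3 points on coverage (√(0.91 × 0.09/100) = 0.029) and about 7% on the SD ratio (1/√200 = 0.07). The first two scenarios are thus compatible with no inflation. The last shows that inflation can survive site adjustment. The latent ICCs are on a different scale from ICC_y, so the two sets of results should not be matched line by line. No calculation was made for the Cox models.

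**The case against.** A reader might infer that the planned intervals are too narrow. The documents do not support that. Inflation needs outcome and procedure choice both to cluster within site after adjustment, and the SAP gives no ICC, cluster size or surgeon-level procedure mix. With procedure choice unrelated to the cluster, the model-based standard error is about right. This stands, and the conclusion is conditional for that reason.

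A reader might also infer that independence rests on the one-outcome argument alone. It does not quite: the sentence conditions on covariates and the next one adds site. In Aim 1, moreover, GEE is introduced as an alternative to the mixed model for weight at several time points. The remark can be read as saying that a repeated-measures tool is not needed for a single binary outcome, which is correct on that narrow point. But the sentence goes further and infers independence between outcomes, which does not follow.

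The SAP does not say whether a node site is one facility or several. If it is one, the site term already covers facility and only the surgeon level is left. The unseen spreadsheet could include a facility term for the Cox models, although a covariate alone would not make the variance cluster-robust.

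Finally, provider ID is not stated to identify the operating surgeon or to be complete, and sandwich standard errors can be unreliable with few or unequal clusters. Both are limits on the remedy and are reflected in it.

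**Conclusion.** The point holds in conditional form. One outcome per patient is not a valid ground for independence between patients. Site is adjusted for, but correlation within a site by facility or surgeon is not addressed for the 30-day composite, and no cluster-robust variance is stated for the Aim 3 Cox models. The standard errors may therefore be too small.

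The central illustration (100 patients per cluster, outcome ICC 0.01) runs from no inflation to 26% as the procedure-choice ICC goes from 0 to 0.6; larger assumed ICCs or clusters give more. None of these inputs comes from the SAP, so the figures show what is possible and do not estimate the error. The quoted sentence concerns one secondary outcome. The extension to the Cox models, which include the Aim 3 primary outcome, rests on what is left unstated there. The point is about precision only. Variation between sites in the procedure effect is a separate matter that neither this argument nor the remedy addresses.

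**What to change.** In Aim 3, Secondary Analysis, delete one outcome per patient as the ground for independence. Keep the logistic and Cox models, the site adjustment and the point estimates. Say whether a node site is one facility or several.

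Report cluster-robust (sandwich) standard errors for the 30-day logistic model and the Aim 3 Cox models. Cluster on facility ID, or on provider ID where it is complete and identifies the operating surgeon. Carry the robust covariance matrix into the delta-method SG versus AGB contrast. Apply a small-sample correction if clusters are few.

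The cost is small: only the variance method changes, and the identifiers are already listed as key variables in Table 1. Their completeness and meaning must be checked at each site first. Intervals may become somewhat wider; if clustering is negligible they should change little.

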## D. AIMS 4-6 (VARIABILITY IN SURGERY OUTCOMES BY BASELINE DEPRESSION, RACE/ETHNICITY, AND AGE)

Aims 4-6 will conduct heterogeneity of treatment (HTE) analyses for primary and secondary outcomes in Aims 1-3. Analytic procedures will be similar to those described above for each outcome's respective aim with a few exceptions noted here. We will not use propensity score adjustment for outcomes in Aims 1 and 2 for the same reasons cited in the analysis plan for Aim 3: that results of our analyses were not affected by propensity score adjustment but the analytic procedures and presentation of results was made more challenging. We will also not repeat sensitivity analyses for Aims 1-3 because they all showed that model findings were robust to the assumptions in question.

For HTE analyses, we will include an interaction between procedure type and the baseline characteristic of interest (depression or race/ethnicity) in the specified regression model. We will conduct ANOVA tests comparing models with and without the interaction to quantify evidence of HTE. Since several outcomes are being examined, we will not have type I error control at  $p < 0.05$  and will consider analyses to be exploratory. Although HTE analyses for Aim 5 (race and ethnicity) and Aim 6 (Age 65+ vs <65) have already been completed for primary outcomes, we will repeat the analyses in the subset of CDRNs that agree to additional analysis of data and we will add the additional secondary outcomes outlined as above.

## HANDLING OF CONFOUNDERS AND MISSING DATA

### A. KNOWN CONFOUNDERS AND UNMEASURED POTENTIAL CONFOUNDERS

The clinically rich information available within CDRNs allows us to adjust for many confounders (e.g., BMI, HbA1c) that are often not available in administrative claims databases. To further minimize unmeasured confounding, we require patients to have non-missing key baseline covariate information for age, sex, and baseline BMI **[CI-4]**. We will use PSs to account for these confounders in the analysis. PSs are a proven method that has been shown to provide valid estimates in observational studies.

Update for Aims 4-6: We will not use propensity score methods in Aims 4-6 to simplify analysis and interpretation of results. Use of propensity score adjustment did not affect results in Aims 1-2, but using propensity score methods made analysis and interpretation challenging. Without propensity score adjustment, we can estimate a single regression model that adjusts for procedure arm (rather than estimating three models for three pairwise comparisons). Pooling information across all three procedures increases the power to identify differences between procedures by adding precision to estimated covariate effects. This approach also simplifies interpretation of findings since it does not produce two (possibly different) estimates of outcome rates at time periods of interest (1, 3, and 5 years) from the two separate pairwise comparison models for that procedure.

### B. MISSING DATA

We require that covariate information on sex, age, and baseline BMI be present for all patients included in the analysis. Some baseline information, including blood pressure, race, and ethnicity may be missing. For blood pressure, we categorized continuous systolic and diastolic blood pressure into a categorical variable indicating hypertension status and included a "missing". For race and ethnicity, we included

“missing” as a possible value for each variable. Sensitivity analyses for Aims 1-3 demonstrated that findings were not sensitivity to excluding people with missing blood pressure, race, or ethnicity information at baseline.

Other covariate information is defined by the presence of particular diagnosis codes or medications in a patient’s medical record and, thus, it is not possible to distinguish between whether a patient is missing particular covariate information (e.g., diabetes diagnosis or insulin prescription) versus a patient who does not have that diagnosis or prescription. There are no missing data methods to adjust for this potential missingness (MD-2). For Aim 1, we conducted a sensitivity analysis that included only data from integrated health systems, where all diagnostic and prescription data are captured through a combination of claims and clinical data, and found that estimated comparisons were similar (MD-4).

Our analyses include a variety of outcome types, including longitudinal, binary, and time-to-event data. Regression models for each make different assumptions about missing outcome information. Mixed effects regression models, used for change in weight (Aim 1) and change in HbA1c (Aim 2) outcomes assume that the observation of the outcome during follow-up is “missing at random” (MAR), that is, that outcome observation is not informative of that outcomes value after conditioning on baseline characteristics and previous observations. In this setting, if a patient is likely to stop getting their weight measured at the onset of a trajectory change (e.g., the patient stops losing weight or begins losing much more weight), then this assumption is violated. There are no missing data methods to address this type of missingness (missing not at random or MNAR) (MD-2). Sensitivity analyses restricted to integrated health systems will include more thorough follow-up since all weight measures will be captured (rather than just weight measurements taken at the health system that performed the bariatric procedure) and, for integrated systems, disenrollment from the health plan would need to be associated with informative missingness for MAR assumptions to be violated (MD-4). Survival analyses with time-to-event data also rely on a MAR assumption: censoring is assumed to be independent of future risk of an event conditional on baseline covariates and observed survival time. Duration of follow-up will be reported for all patients (MD-3).

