### A. AIM 1 (WEIGHT LOSS AND WEIGHT REGAIN)

To what extent does weight loss and weight regain differ across the three bariatric surgical (RYGB, AGB, and SG) at 1, 3, and 5 years?

Primary Analysis: Complete three pairwise comparisons (RYGB vs. AGB; RYGB vs. SG; AGB vs. SG) for our primary and secondary outcomes and all sensitivity/heterogeneity analyses on adults  $\geq 20$  years of age using *individual-level data with multiple imputation for missing weight data after surgery*

Secondary Analysis: Complete three pairwise comparisons for our primary and secondary outcomes and all sensitivity/heterogeneity analyses using *distributed data analysis approach*

Primary Outcome: percentage change in weight (in kg) at 1, 3, and 5 years compared to baseline

Secondary Outcomes: 1) weight regain at 3 and 5 years; estimated as percent regain from the maximum weight (in kg) loss in the first 2 years; 2) a post-operative body weight that is  $<5\%$  lower than the pre-surgical weight at 1, 3, or 5 years after bariatric surgery; and 3) proportion achieving  $>5\%$ ,  $>10\%$ ,  $>20\%$ , and  $>30\%$  weight loss at 1, 3, and 5 years

Sensitivity Analyses (for primary outcome): 1) Calendar Year analysis: look at the effects of these procedures on weight changes by calendar year

Heterogeneity Analyses (for primary outcome): 1) Complete all analyses on adolescents  $<20$  years of age; 2) Compare comorbidity groups (e.g., baseline diabetes) or comorbidity index score quartiles 3) Compare baseline BMI ( $\geq 50$  vs  $<50$  kg/m $^2$ ), 4) Compare adults  $<65$  years and 65+ years; 5) Compare race/ethnicity (e.g., non-Hispanic black, Hispanic, non-Hispanic white), 6) Gender (male vs. female)

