## ANALYTIC PLANS BY AIM

**Descriptive analysis:** The study team will develop a distributed program to create the study cohort based on the eligibility criteria described above. The distributed program will also compare the baseline characteristics of the study cohort with patients who are otherwise eligible for the study but have missing information in key baseline covariates [CI-1, CI-2] (e.g., baseline BMI, and HbA1c among patients with diabetes). The comparison will allow us to assess the representativeness of the study cohort and help explore possible selection bias that can later be addressed in the analysis and interpretation of the study results. This descriptive analysis is different from the study data characterization that will be done prior.

We will characterize and compare eligible patients who undergo the three bariatric procedures in detail. Specifically, we will compare the distributions and missingness of the baseline covariates, the length of follow-up and missingness in post-surgery outcome measures (e.g., changes in BMI and HbA1c among patients with diabetes) [IR-1]. For Aim 5, we will examine differences between patients with and without race and ethnicity information.

A key consideration for observational comparative effectiveness studies is to include only patients who are eligible to receive the alternative treatments being compared. We will assess such “empirical equipoise” by examining the degree of overlap in the distributions of the estimated propensity scores for each of the three pairwise comparisons (described in detail below) [CI-5]. The comparisons will help us identify patients who may have certain characteristics or contraindications that disqualify them from receiving one or more of the three studied bariatric procedures in typical clinical practice. We will restrict the study cohort to patients in the overlapping region of the propensity score distributions as appropriate.

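### The SAP wrongly says nothing can address outcomes missing not at random, and plans no analysis of percent weight change that relaxes MAR

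*SAP*

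**What the plan says.** In the SAP, Handling of Confounders and Missing Data, B. Missing Data, the mixed models for weight and HbA1c are said to assume MAR given baseline covariates and earlier measurements. The section then gives an example that would break this: patients cease to be weighed when their course changes, in either direction ("the patient stops losing weight or begins losing much more weight"). It concludes: "There are no missing data methods to address this type of missingness (missing not at random or MNAR").

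The remedy offered is a sensitivity analysis restricted to integrated health systems, where the SAP argues that "disenrollment from the health plan would need to be associated with informative missingness for MAR assumptions to be violated".

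Other places bear on the point:

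- The Aim 1 synopsis plans "multiple imputation for missing weight data after surgery", and the Aim 1 primary analysis says "We will apply the analysis procedure to each imputed dataset", followed by the usual combining rules. The Missing Data section does not mention imputed weights.
- The descriptive analysis will compare "the length of follow-up and missingness in post-surgery outcome measures" between procedures.
- Analytic Plans by Aim, D. Aims 4-6, says: "We will also not repeat sensitivity analyses for Aims 1-3 because they all showed that model findings were robust to the assumptions in question".
- Table 1 ends the data in 2016, described as "one year after the last bariatric procedure (2015) in the study".

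**The concern.** Two statements are wrong, and together they leave a gap in the analysis of the Aim 1 primary outcome.

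First, MNAR cannot be identified from the observed data, but it can be examined under stated assumptions. That it cannot be tested is the reason for a sensitivity analysis, not a reason to omit one.

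Second, an integrated system captures every weight that is taken. It does not ensure that every enrolled patient is weighed. The VITAL entry in Table 1 holds recorded values only, so an enrolled patient who stops attending leaves no weight. If attendance depends on the current, unseen weight, MAR fails without disenrollment. This is the mechanism that the same section describes a few sentences earlier.

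The risk is that agreement between the full cohort and the integrated subset is taken as evidence about MAR when both analyses assume it. Mean weight loss per procedure at 3 and 5 years can be biased even when missingness is alike across procedures. The pairwise difference is biased mainly when missing fractions, or departures from MAR, differ by procedure. For Aims 4-6, the bias in a procedure-by-subgroup interaction cancels only if the pairwise bias is the same in each subgroup.

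**Working it through.** **Does any planned analysis relax MAR for weight?** These are the analyses in the SAP that bear on missing data or robustness for Aim 1:

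| Analysis | Where | Relaxes MAR for the outcome? |
|---|---|---|
| Multiple imputation of weights | Aim 1 synopsis and primary analysis | No; no departure from MAR is specified |
| Mixed model | Missing Data | No; MAR is stated |
| Effects by calendar year | Aim 1 synopsis | No |
| Distributed analysis | Aim 1 secondary analysis | No |
| Patients without a baseline BMI | Inclusion criteria | No; concerns baseline |
| Excluding missing blood pressure, race or ethnicity | Missing Data | No; concerns baseline |
| Integrated systems only | Missing Data | No; a MAR model in a subset |
| Missingness by procedure | Descriptive analysis | No; describes it without showing its effect on estimates |

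**Can MAR fail with no disenrollment?** A simulation on assumed inputs serves as a counterexample. It has 400,000 patients per procedure, all enrolled throughout.

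- Mean weight change at years 1 and 3 is -28 and -24 in procedure A, and -22 and -18 in B. The year-1 SD is 8.
- Year 3 depends on year 1 with slope 0.8 and residual e of SD 6.
- The log-odds of being weighed at year 3 are 0.3 - b·e, with b = 0.15 in A and 0 in B.
- Missing year-3 weights are predicted from year 1 under MAR.

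Results: 44% (A) and 42% (B) are unweighed. A has a true mean of -24.01 and a MAR estimate of -26.03; B has -17.97 and -17.98. The true difference is -6.04 and the MAR estimate is -8.06, an error of about 2.0 points. This refutes the claim that disenrollment is necessary. It does not estimate the bias in this study.

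**How large could the effect be?** The SAP states no figure to reproduce and gives no missing fractions. Let m be the fraction unweighed among patients who could reach the visit, and d the points by which MAR overstates their weight loss. Both are assumed. The mean loss of a procedure is then overstated by m × d, and the pairwise difference is off by m1·d1 - m2·d2.

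| m1, m2 | d1, d2 | Per procedure | Pairwise |
|---|---|---|---|
| 0.5, 0.5 | 5, 5 | 2.5 and 2.5 | 0 |
| 0.5, 0.5 | 5, 2 | 2.5 and 1.0 | 1.5 |
| 0.5, 0.3 | 5, 5 | 2.5 and 1.5 | 1.0 |

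Signs reverse if unweighed patients lose more than MAR predicts.

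**Would the integrated subset reveal it?** Suppose m falls to 0.3 there, with d still 5 and 2. The pairwise error is 0.3 × (5 - 2) = 0.9, against 1.5 in the full cohort. The two estimates differ by only 0.6 and could look similar while both are biased.

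**Which patients should a delta apply to?** Surgery years run 2005-2015 (11 years), and the data are taken to run through the end of 2016. Year + 5 ≤ 2016 holds for 2005-2011, so 4 of 11 years (36%) cannot reach 5 years. Year + 3 ≤ 2016 holds for 2005-2013, so 2 of 11 (18%) cannot reach 3 years. This is administrative truncation, not informative drop-out. Assume equal surgeries per year and 40% unweighed among reachable patients. If unreachable patients were also imputed and shifted at 5 years, the unmeasured fraction would be 4/11 + 7/11 × 0.4 = 0.618. A delta of 5 would then move the mean by 3.09 points instead of 0.4 × 5 = 2.0.

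**The case against.** The strongest reply is that the sentence on methods can be read as shorthand: no method removes MNAR bias from observed data without untestable assumptions. The next sentence does offer a sensitivity analysis, so the SAP does not simply give up. That is fair, and the integrated-system restriction is a real mitigation: in the example above it cuts the pairwise error from 1.5 to 0.9. But the sentence does not say what the charitable reading needs, and the analysis that follows still assumes MAR.

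It is also true that non-attendance alone does not break MAR. It does so only if attendance depends on the unseen weight after conditioning on covariates and earlier weights. This narrows the point without removing it, because the SAP's own example is of that kind. A model that conditions on many recorded weights would leave less bias than the simulation, which used year 1 only and built the violation in.

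On Aims 4-6, the robustness sentence most naturally means the assumptions that were examined, and those aims are declared exploratory. Rewording is therefore enough there if a further analysis is not wanted.

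Finally, every magnitude is assumed, and a delta grid chosen now would follow known Aim 1 results. Both are true. The first means that no particular bias can be claimed; the second means that the analysis must be labelled accordingly.

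**Conclusion.** The concern holds. Both statements in the Missing Data section are wrong as written, and no analysis in the SAP relaxes MAR for percent weight change. Whether the results are biased, and by how much, cannot be determined from the document. Under the assumed missing fractions of 30-50% and departures of 2 to 5 points tabulated above, the pairwise error ranges from 0 to 1.5 percentage points in either direction, and the per-procedure error reaches 2.5. The claim that the integrated-system comparison cannot settle the matter needs none of these inputs: it follows from both analyses assuming MAR. This should be corrected, but it does not by itself invalidate the primary analysis.

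**What to change.** 1. Delete the sentence on methods. Say instead that MNAR cannot be identified from the data and is examined by sensitivity analysis.
2. State that MAR can also fail in integrated systems when enrolled patients stop being weighed for reasons tied to their current weight, and that the restricted analysis still assumes MAR. Keep it as an additional check.
3. Reconcile the Aim 1 text on multiple imputation with the Missing Data text on mixed models, so that it is clear whether weights are imputed.
4. Add a delta-adjusted (tipping-point) analysis of percent weight change, chiefly at 3 and 5 years. Use procedure-specific deltas over a stated grid in both directions, for example -10 to +10 points, equal and unequal across procedures. Apply them only to patients whose surgery date allows the time point before the data end.
5. Report missing fractions by procedure, split into administrative and other, and the delta at which each pairwise conclusion changes.
6. For Aims 4-6, either apply the same analysis to weight or reword the robustness sentence so that it does not suggest MAR was tested. Extending this to HbA1c is optional and would need its own imputation step.

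The cost is SAP wording, modest programming and one further sensitivity table. If the mixed model was fitted to observed weights only, an imputation step must be built first. The SAP already reports Aims 1-2 findings as known, so the Aim 1 analysis should be labelled as added later.
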